Sample Size Power Analysis: Aim 1&2, H1.1-H1.2 & H2.1 estimates of statistical power are based on Aim 1 and initially the primary outcome of pain. Whereas dyad is the unit of randomization, we assess power based on separate analyses for Veterans and partners (one approach used). There are 4 major intervals of assessment (baseline, 1, 2, and 4-months). At the beginning of this study, we estimated attrition based off of a previous MR trial that had less than 5% attrition. Based on early recruitment at the primary site, we have adjusted recruitment goals to allow for approximately 33% attrition, and uneven recruitment across the three study sites. Assuming within-subject (outcome measurement) correlation of 0.5, the proposed sample size will provide 80% power (2-sided type I error rate of 0.05) to detect a “small-to-medium” effect size of 0.38 (Cohen’s d). For analyses stratified by site (in addition to evaluation by random effect assessment), the study will provide 80% power to detect a “medium-to-large” effect size of 0.66. By way of comparison, the pilot data presented above describes large effect sizes ($d = 0.81$ for pain symptom reduction). While this effect size was based on a relatively small sample of comparable patients ($n < 15$) and within-subject assessment (paired t -test), it provides good assurance that the proposed sample size is sufficient to detect realistic, medium size effects should they exist with the MR program. For secondary outcomes, we will use a type I error rate of 0.01 for multiple comparisons. For the sample and our described assumptions, this will provide 80% power to detect a “medium” effect size of 0.45.⁵⁹

Sample Size: Qualitative- Aim 3 sample size relies on the quality and richness of information obtained.⁶⁰ Conceptual saturation is the goal of qualitative research, and depends on data to support interpretations. Saturation has been noted to occur within the first 12 interviews.^{60,61} Our team has extensive experience in evaluating electronic technologies, and have found recruiting high and low volume users provides the richest dataset. To ensure representative data, we will conduct telephone interviews with a purposive (e.g., high or low MR utilization group) sub-sample of up to 84 individuals to achieve representation at each site (approximately 28 individuals/site).

Data Collection Procedures. Data will be collected using (1) self-report surveys; and (2) telephone interviews.

(1) Self-reported Survey Data.

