TBI Exposure	OHIO TBI Exposure Screen ⁶⁴	8-items designed to elicit self- or proxy-reports of TBI occurring over a person's lifetime. Can provide measures of the extent of exposure to TBI including the current injury.	5	Pre-screening
Veteran and Partner Independent Variables				
Demo-graphics	Participant Survey	15-items assess age, gender, ethnicity/race, education, income levels, religion, marital status, relationship length, military service/status/grade, deployments, computer/internet use.	5	Baseline
Veteran Independent Variable – Covariate				
Other Treatments	Concurrent treatments	2 items asking Veterans to report concurrent pain and PTSD treatment(s) and CIH modalities to account for dual intervention effects.	1	Baseline, months 1, 2, 4
Veteran Dependent Variables				
Quality of Life	Self-Assessment of Change ^{62,63}	16-item word pairing scale to assess a variety of shifts in well-being across a broad range of therapeutic modalities and conditions.	5	months 1, 2, 4

Quality of Life	Quality of Life SF12 ⁶⁵	12-items to assess quality of life using physical status and mental health distress.	3	Baseline, months 1, 2, 4
Pain	Defense and Veterans Pain Rating Scale ⁶⁶	10-point scale to measure “usual” pain intensity over the last week and 4 pain functionality (past month) items.	3	
	Pain Outcomes Questionnaire e- Short Form VA ⁶⁷	20-items assess pain-related domains, including pain intensity, interference with activities and mobility, negative affect, vitality, pain-related fear; and improbable pain-related symptoms.	5	
Pain	Single item scale	One item will assess pain using a 0 to 5-point Likert-type scale.	1	Baseline, weeks 1-8; months 1, 2, 4
Stress and Tension	Single item scales	Two items will assess stress and tension using a 0 to 5-point Likert-type scale.	1	
PTSD & Related Psychological Symptoms	PTSD: Posttraumatic Checklist ⁶⁸	20-item measure of the DSM-V PTSD symptoms with scales related to stress, anxiety, & emotional numbing.	4	Baseline, months 1, 2, 4
	Depression: Beck Depression Inventory ⁶⁹	21-items, a widely used instrument for measuring depression. Respondents are asked to rate their symptoms and attitudes using a 4-point scale.	5	
	Stress: Perceived Stress Scale ⁷⁰	10 Likert-scaled items, validated and widely used, to determine perceived stress levels.	3	

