Hypotheses Aims 1 & 2. All outcome measures (*primary and secondary*) under Aim 1 will be collected at baseline, 1, 2, and 4 months and are continuous variables. Therefore, general linear mixed models will be used with main effects terms for GROUP (MR vs. waitlist) and TIME (4-time points) and a GROUP x TIME interaction term (for rate of change). The models will also include site as a random effect. To assess whether the rate of change is curvilinear (i.e., the rate of change differs between time points), a quadratic parameter will be tested. Different correlation structures and functional forms of the effects of the MR program will be assessed using the information criteria and a final parsimonious model will be determined for final statistical inference. Initial effects of the MR program (baseline to 1-month) will be evaluated by analysis of covariance (ANCOVA). For H1.1, the primary outcome measure for pain will be total score on the 19-item POQ. For H1.2., the primary outcome measure for PTSD will be total score on the 20-item PCL-5. Subgroup analyses will be explored using similar methods and examination of severity of baseline pain and PTSD scores. These analyses will provide insight into subgroups in whom the MR program may be particularly beneficial. In a similar realm, analyses will be stratified by baseline median level of relationship satisfaction, as derived from total score on the 14-item RDAS. This will permit assessment of the effect of the MR intervention on potential improvement in relationship satisfaction among a cohort of dyads with presumably troubled relationships at entry. Moreover, using the weekly reports (8 weeks) of MR use and satisfaction with the MR program, the MR sample will be split above versus below the median for these two measures, and compared separately against the waitlist control condition at 2-months. This approach approximates a “per protocol” analysis in terms of recommended use of the MR program. In addition, especially for Aim 2 outcomes, we seek to examine whether dyads appear to show mutual benefits from the MR program. Therefore, multilevel models will be fit using an over-time dyadic model⁷⁸ in which individuals are nested within dyads and time is crossed with dyads (i.e., both Veteran and partner are assessed at the 4 time points). This analysis accounts for the non-independence due to the correlation between dyad members’ general levels on outcomes averaged over time, as well as the time-specific correlation between their outcomes (e.g., similarity caused by time-specific events).

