Different correlation structures and functional forms of the effects of the MR program will be assessed using the information criteria and a final parsimonious model will be determined for final statistical inference. For H1.1, the primary outcome measure for pain will be the total score on the 19-item POQ, and its subscales. Additional analyses will be performed on the DVPRS, and the weekly 5-point Likert-scale Pain item. For H1.2, the primary outcome measure for PTSD will be total score on the 20-item PCL-5. For H1.2, the outcome measure for psychological symptoms is PSS; the outcome measure of sleep is PSQI; and the outcome measure for QOL is the SF12 and BDI. For H2.1, the outcome measure for relationship satisfaction is the RDAS. Additional analyses will be performed on the COS and CSS measures, the weekly 5-point Likert-scale Stress item, and the weekly 5-point Likert-scale Tension item.

Qualitative data analysis followed Inductive and deductive coding methods. A qualitative code book, consisting of known constructs from the literature and those that emerged inductively from the data, was created. Two trained qualitative researchers coded the data using the qualitative analysis software program, ATLAS.ti v. 22. To establish intercoder reliability at 80%, two qualitative researchers coded 20% of the interviews (initially every 5th transcript then randomly to ensure coding consistency) separately then compared codes to determine percent of agreement. Coded text in ATLAS.ti v. 22 was exported and further analyzed in Excel spreadsheets to develop themes. To enhance credibility, initial findings were presented during quarterly stakeholder meetings to provide input and facilitate refinement of findings.

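### The Updated SAP adds the POQ subscales to the H1.1 primary measure without saying whether a subscale can decide H1.1; the protocol names the total score alone

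*Combined protocol and SAP*

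**What the plan says.** The primary pain measure is defined twice. In the protocol (Data Analysis, Hypotheses Aims 1 & 2), "the primary outcome measure for pain will be total score on the 19-item POQ". In the Updated Statistical Analysis Plan, "the primary outcome measure for pain will be the total score on the 19-item POQ, and its subscales". The SAP then opens a separate tier: "Additional analyses will be performed on the DVPRS, and the weekly 5-point Likert-scale Pain item". The POQ subscales are not in that tier.

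The protocol's Sample Size Power Analysis supplies the error rates. There, "estimates of statistical power are based on Aim 1 and initially the primary outcome of pain", and "the proposed sample size will provide 80% power (2-sided type I error rate of 0.05) to detect" a standardised effect of 0.38. The only multiplicity rule is in the same section: "For secondary outcomes, we will use a type I error rate of 0.01 for multiple comparisons". The aims label H1.1 as the primary outcome, in the singular, and H1.2 and H2.1 as secondary outcomes.

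No section says which POQ subscales are meant, how many are scored, at what level they are tested, or whether one of them can support H1.1.

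**The concern.** The SAP's sentence is almost the protocol's sentence with the subscales added, and the addition falls inside the definition of the primary measure. Suppose the POQ total shows no significant difference and one subscale favours MR. One analyst could call H1.1 unsupported, citing the protocol. Another could call it supported, citing the SAP. Nothing in the plan settles the matter between them.

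The stake is the error rate of the trial's only primary hypothesis. The power section provides for one pain outcome at 0.05 and makes no allowance for several scores that could each carry the claim. The 0.01 level would limit the problem if it applied, but it is stated for secondary outcomes, and the plan does not say whether subscales named in the primary sentence count as secondary.

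**Working it through.** **The plan's own figure.** Two-sided 0.05, 80% power, d = 0.38, 1:1 allocation, standard deviation 1:

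n per arm = 2 × (1.960 + 0.842)² / 0.38² = 2 × 7.85 / 0.1444 ≈ 109, or 218 evaluable dyads.

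The 600 dyads in the protocol less 33% leave about 402, or 201 per arm. Power at d = 0.38 is then Φ(0.38 × √(201/2) − 1.960) = Φ(1.85) ≈ 96.8%, not 80%. The stated figure is therefore not reproduced at the stated sample size. That is a separate matter; what counts here is that the calculation is for one comparison at two-sided 0.05.

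**Inputs for the error rate**
- Level for the primary outcome: two-sided 0.05, critical value 1.960 (Sample Size Power Analysis).
- Level for secondary outcomes: 0.01 (same section), taken as two-sided, critical value 2.576.
- Number of subscales k: not given. Table 1 describes the instrument thus: "20-items assess pain-related domains, including pain intensity, interference with activities and mobility, negative affect, vitality, pain-related fear; and improbable pain-related symptoms". That suggests 5 or 6 substantive domains, depending on whether activities and mobility count as one or two, with improbable symptoms left out. Assumed: 5 and 6.
- Correlation r between subscale test statistics: not given. Assumed: 0.3, 0.5 and 0.7.
- Total score: assumed to be the equal-weight sum of the subscales.

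**Model with no true effect**
- Subscale statistics: Zᵢ = √r · W + √(1 − r) · Eᵢ, for i = 1 to k, with W and Eᵢ independent standard normal.
- Total: T = ΣZᵢ / √(k + k(k − 1)r).
- Positive values favour MR. Each cell below rests on 4,000,000 draws.
- Reference: for the total alone, P(T > 1.960) = 2.5%.

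**Reading A: any score at two-sided 0.05 can carry H1.1.**

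| k | r | Any score favourable | Subscale favourable, total not significantly so |
|---|---|---|---|
| 5 | 0.3 | 10.8% | 8.3% |
| 5 | 0.5 | 9.2% | 6.7% |
| 5 | 0.7 | 7.4% | 4.9% |
| 6 | 0.3 | 12.4% | 9.9% |
| 6 | 0.5 | 10.4% | 7.9% |
| 6 | 0.7 | 8.2% | 5.7% |

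The columns agree: the first equals the second plus 2.5%, for example 9.9% + 2.5% = 12.4%. If false positives in either direction are counted, a separate run of 1,000,000 draws per cell gives 14.9% to 24.5%, against 5% for the total alone.

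**Reading B: total at two-sided 0.05, subscales at the 0.01 secondary level.**

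| k | r | Any score favourable | Subscale favourable, total not significantly so |
|---|---|---|---|
| 5 | 0.3 | 3.8% | 1.30% |
| 5 | 0.5 | 3.3% | 0.85% |
| 5 | 0.7 | 2.9% | 0.38% |
| 6 | 0.3 | 4.1% | 1.63% |
| 6 | 0.5 | 3.6% | 1.06% |
| 6 | 0.7 | 3.0% | 0.49% |

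The ambiguity therefore matters under Reading A and has little effect under Reading B.

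**The case against.** The case for a harmless reading is good. The SAP speaks of a measure in the singular, puts the total first and adds the subscales after a comma. The protocol names the total alone, the aims label one primary outcome, and the power section sizes the trial for one. The Updated SAP is short: it restates no alpha, intention-to-treat or missing-data rule and refers back to the protocol's Table 1. It can be read as supplementing the protocol, in which case the protocol's definition still governs. All of that stands and makes the total-only reading the likelier one. It does not close the question, because the SAP does not say that it supplements the protocol, and its list of additional pain analyses omits the subscales.

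Four stronger inferences are tempting, and the documents do not support them.

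- A reader might infer that the SAP makes the subscales co-primary or permits H1.1 to be claimed on one of them. It states no decision rule at all. It only fails to exclude such a claim.
- A reader might contrast the PTSD sentence, "For H1.2, the primary outcome measure for PTSD will be total score on the 20-item PCL-5", which has no subscales, and infer a deliberate change for pain. The contrast is weak. H1.2 is labelled secondary, so the plan also uses the phrase for the main instrument of a construct. The SAP also pairs the SF12 and BDI under quality of life without ranking them.
- A reader might infer that the choice will be made once results are known. Nothing documents this; the quantitative part of the SAP is written in the future tense.
- A reader might take the item count (20 in Table 1, 19 in both definitions) as showing that the primary total is undefined. It is a separate clerical discrepancy and does not show that.

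**Conclusion.** The point holds as an unresolved discrepancy over the primary measure. The protocol gives H1.1 one deciding score; the SAP adds subscales to the same sentence and assigns them no role.

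The size depends on a rule the plan does not give. Under Reading A, the chance of a false positive favouring MR is about 7% to 12%, against 2.5%. Under Reading B, the conflict between a favourable subscale and a total that is not significantly favourable arises in about 0.4% to 1.6% of null trials. Both ranges rest on an assumed 5 or 6 equicorrelated subscales, assumed correlations of 0.3 to 0.7 and an equally weighted total. Confidence is high about the difference in wording and lower about its consequence. It should be fixed because it concerns the only primary hypothesis and the repair is small.

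**What to change.** In the Updated SAP, name the POQ total score as the sole primary outcome for H1.1, tested at two-sided 0.05, in line with the protocol's Data Analysis and Sample Size Power Analysis sections. List the POQ subscales with the DVPRS and the weekly pain item as supportive analyses that cannot carry H1.1.

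The cost is SAP wording only: no new data and no change to the basis of the power calculation. The downside is that a positive subscale alone can no longer support H1.1.

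An alpha-sharing or hierarchical rule would also remove the ambiguity. Equal Bonferroni sharing is the dearer route: across 6 or 7 scores (the total plus 5 or 6 subscales) each test would run at 0.05/6 = 0.0083 or 0.05/7 = 0.0071. The number needed per arm for d = 0.38 would rise from 109 to 168 or 173, and power at 109 per arm would fall from 80% to about 57% or 55%.

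Separately, reconcile the POQ item count between Table 1 and the two definitions. This change does not settle which model term or time point decides H1.1.

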METHODOLOGY: The specific aims are to: **(Aim 1)** Determine MR effectiveness for physical (pain, sleep), PTSD (intrusion, arousal, avoidance, numbing), and psychological (depression, stress, anxiety) symptoms, and global health (quality of life); **(Aim 2)** Determine MR effectiveness for social (relationship satisfaction, compassion for self/others) outcomes among Veterans and their partners; and **(Aim 3)** Describe Veteran and partner perceived value of MR in a sub-sample of participants. The sample will consist of Veteran and partner dyads (N = 600). **Aim 1 & 2** data collection will include self-report assessment of 4-data points over a 4-month period to evaluate physical, psychological, and social outcomes. Eight weekly reports will also be collected for the first two months of MR use to assess MR utilization, and pain and stress levels. **Aim 3** data collection will include telephone interviews from a selected sub-sample of 84 individuals to examine MR user experiences, study experiences, and to collect their suggestions for making MR useful for Veterans and their partners.

CLINICAL RELEVANCE: In a community-based trial in a non-clinically defined sample of Veterans, MR was associated with significant reductions in pain and PTSD-related symptoms. In the proposed study we will test MR's effects in a clinically defined population as a complement to clinical services. This program evaluation is needed to determine MR's appropriateness for implementation within the VA for clinically defined populations.

Aim 1: Determine MR effectiveness for physical (pain, sleep), PTSD (intrusion, arousal, avoidance, numbing), and psychological symptoms (depression, stress, anxiety), and global health (quality of life).

H1.1. Veterans who use MR will report significantly greater improvement in physical pain compared to those in the control group. (Primary Outcome)

H1.2. Veterans who use MR will report significantly greater improvement in PTSD and psychological symptoms, sleep and quality of life compared to those in the control group. (Secondary Outcomes)

Aim 2: Determine MR effectiveness for social (relationship satisfaction, compassion for self/others) outcomes among Veterans and their partners.

H2.1. Veterans and partners who use MR will report significantly greater improvement in social outcomes compared to the control group. (Secondary Outcomes)

Aim 3: Describe Veteran and partner perceived value of MR in a sub-sample of participants.

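### H1.1 claims an effect on physical pain, but its POQ measure also scores mood, vitality and fear, and no rule ties the conclusion to a pain score

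*Combined protocol and SAP*

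**What the plan says.** The specific aims word the primary hypothesis as "Veterans who use MR will report significantly greater improvement in physical pain compared to those in the control group". Aim 1 groups pain with sleep as physical symptoms and lists depression, stress and anxiety separately as psychological. H1.2 makes PTSD, psychological symptoms, sleep and quality of life secondary.

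Two places define the measure for H1.1:

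- Protocol, Data Analysis (Hypotheses Aims 1 & 2): "the primary outcome measure for pain will be total score on the 19-item POQ".
- Updated Statistical Analysis Plan: "the primary outcome measure for pain will be the total score on the 19-item POQ", and the same sentence goes on to add the POQ subscales.

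Table 1 describes the instrument: "20-items assess pain-related domains, including pain intensity, interference with activities and mobility, negative affect, vitality, pain-related fear; and improbable pain-related symptoms".

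The updated SAP places the DVPRS and the weekly single pain item under additional analyses. Neither document gives the scoring of the POQ total, the number of items per domain, or an order of testing between the total and its subscales. Neither requires a pain score to improve before H1.1 is declared met.

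**The concern.** The hypothesis names one construct and the score that decides it covers several. Negative affect and pain-related fear lie close to the depression, stress and anxiety that H1.2 treats as secondary, and vitality is not pain either. MR teaches meditation and positive psychology as well as massage, and the Background cites effects of these methods on stress, anxiety and depression. The non-pain domains are therefore plausible targets of the programme in their own right.

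The updated SAP adds a second route. It names the total and the subscales together as primary, with no hierarchy, so a result on the negative-affect subscale alone could be cited as support for H1.1.

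What is at stake is the wording of the main conclusion. The protocol plans to present MR as a chronic pain management option and to brief pain clinicians on it. Under the present text, a result driven by affect, vitality or fear could be reported as a reduction in physical pain, and H1.1 and H1.2 could partly report the same effect twice.

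**Working it through.** **Do the non-pain domains enter the total?** Table 1 counts 20 items and the analysis sections count 19. If both describe the same form, at most one item is dropped. One item cannot remove all three of the affect, vitality and fear domains, so the total is a mixed score whichever item is left out.

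**Which sample sizes are relevant?** The documents support more than one, so the illustration uses three.

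- From the stated d = 0.38 (80% power, two-sided 0.05; Sample Size Power Analysis): n = 2 × (1.960 + 0.842)² / 0.38² = 108.7, so 109 per arm. With the stated within-subject correlation of 0.5, the change-score variance is 2 × (1 − 0.5) = 1, so the change score gives the same n.
- From 600 dyads (Study Design and Overview) less 33%: 600 × 0.67 / 2 = 201 per arm. The detectable d there is 2.802 × √(2/201) = 0.28, not 0.38. That mismatch is a separate matter.
- From the 200 dyads in the Sample section, which speaks of Tampa, less 33%: 200 × 0.67 / 2 = 67 per arm. This is a low bound.

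**Domain-level illustration.** Assumptions, none of them in the documents: six equally weighted, unit-variance domains (interference split into activities and mobility, improbable symptoms left out) with common correlation r. Affect, vitality and fear each shift by 0.5 SD, and the other three shift by 0.

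- SD of the sum = √(6 + 30r)
- d of the total = 3 × 0.5 / √(6 + 30r)
- Power = Φ(d × √(n/2) − 1.96), for a simple two-group comparison

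| r | SD of sum | d of total | n = 67 | n = 109 | n = 201 |
|---|---|---|---|---|---|
| 0.3 | √15 | 0.387 | 0.61 | 0.82 | 0.97 |
| 0.5 | √21 | 0.327 | 0.47 | 0.68 | 0.91 |
| 0.7 | √27 | 0.289 | 0.39 | 0.57 | 0.82 |

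With a shift of 0.3 SD instead, power is 17–27%, 25–40% and 41–64% at 67, 109 and 201 per arm.

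**Item-level illustration.** Take 19 equally weighted, unit-variance items with common correlation ρ, of which m non-pain items shift by 0.5 SD and the rest by 0. Then d = 0.5m / √(19 × (1 + 18ρ)).

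- m = 6, ρ = 0.5: d = 3 / √190 = 0.22. Power is 36% at 109 and 59% at 201 per arm.
- m = 10, ρ = 0.3: d = 5 / √121.6 = 0.45. Power is 92% at 109 and over 99% at 201 per arm.

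The result is driven by m, ρ and n. The documents give neither m nor ρ, and they give more than one n.

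**The case against.** The strongest reply is that the POQ total is a reasonable pain outcome. Table 1 files it under pain and describes all its domains as pain-related. The protocol rests on a biopsychosocial model with a two-way link between pain and PTSD, which suits a multidimensional measure. In Aim 1, physical is a grouping word for pain and sleep. This stands as a defence of the instrument. It does not defend a conclusion about physical pain drawn from the total alone.

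Second, pain is also measured more directly. The POQ subscales, the DVPRS and the weekly pain item are all to be analysed, so an effect confined to mood would be visible. This also stands. A reader might infer that the trial could not support MR as a pain intervention, but the documents do not bear that out. The pain measurements exist; what is missing is a rule linking them to the H1.1 conclusion.

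Third, the illustration rests on guesses. Equal weights, exactly zero effect on pain and a two-group test are all assumptions. The planned analysis is a mixed model with a GROUP x TIME term, and the protocol's own theory argues against a complete split between pain and mood. A reader who saw only the 201-per-arm row might infer that a false pain claim is likely. The smaller sample sizes and the 6-of-19-item case show that the documents support a possibility and not a probability.

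**Conclusion.** The mismatch is real and should be corrected. H1.1 is stated for physical pain; its measure is a mixed total in the protocol, and that total plus unordered subscales in the updated SAP. H1.1 can therefore be declared met without a change in pain intensity or interference. The test of the total itself remains valid; the stated conclusion may not follow from it.

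The size cannot be fixed from the documents. Under the assumptions shown, a 0.5 SD effect confined to three of six domains gives a total d of 0.29–0.39, with power from 39% to 97% across the three sample sizes. The item-level cases run from d = 0.22 to 0.45.

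A reader might also infer from the 20 and 19 item counts that the improbable-symptoms content is what was left out. No text says so; the documents show only that the two counts differ.

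**What to change.** 1. Make the POQ total the single primary test at two-sided 5%. Remove the subscales from the primary definition in the updated SAP, so that it agrees with the protocol's Data Analysis section.
2. State the H1.1 conclusion as an effect on pain-related impairment (POQ total).
3. Name the POQ pain-intensity and interference subscales as key secondary scores in a fixed order. Test them only after a significant total, at the same time point and with the same contrast, and report them beside it. Base any claim about pain itself on these scores. If each step is tested at 5% and testing stops at the first non-significant result, the error rate over the chain stays at 5%. Say explicitly that this chain stands apart from the 0.01 level set for the other secondary outcomes.
4. Reconcile the 20-item and 19-item counts and list the items that enter the total, without assuming which one is omitted.

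The cost is text only, since the subscales are already to be analysed. A result driven only by affect, vitality or fear could no longer be reported as a reduction in physical pain. A claim about pain would need more than one significant test, so it is somewhat harder to reach. The order also matters: a benefit on the later score is not formally tested if the earlier one fails. The rule should be set before outcomes by arm are seen; if they have been seen, report it as a limit on interpretation.
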